U-500 regular insulin (U-500R) is a five-fold concentrated form of insulin (contains 500 units of insulin per mL) for the treatment of T2DM patients with severe insulin resistance (T2DM conditions that require >200 units of insulin per day). It was first approved in 1994 by the United States Food and Drug Administration (FDA).^{3,4} To avoid dosing errors, it is currently available for administration through pens and vials with the dedicated U-500R syringe.⁵ In addition, off-label continuous subcutaneous insulin infusion (CSII) administration has been employed increasingly for the administration of U-500R.⁶ The high concentration of insulin in U-500R allows the administration of high doses, at 20% of the volume of a corresponding dose of U-100, which leads to improved subcutaneous depot absorption.^{1,7} In addition, high doses of insulin may be achieved with twice or thrice-daily administrations of U-500, which mitigate physical discomfort and potential barriers to adherence associated with U-100.^{4,8} Furthermore, the increase in insulin at subcutaneous depots increases the formation of insulin hexamers, which prolong the duration of the hypoglycemic effect of insulin therapy.

U-500R use has been shown to improve glycated hemoglobin (HbA1c) levels among T2DM patients who switched from U-100 to U-500R.⁷ U-500R use has also been found to be associated with lower health care costs and better adherence than U-100 users prescribed a similar dose.^{9,10} Previous research suggests that T2DM patients who initiated therapy with an insulin pen are more adherent to treatment than those using the vial/syringe method.¹¹ Insulin pen devices have also been shown to provide more reliable, accurate, and simplified dosing than vial/syringe administration.^{11,12} However, little is known on treatment patterns, treatment outcomes and economic burden of the U-500R administration in the real-world setting. Therefore, STATinMED Research will use real-world data to evaluate treatment patterns, treatment outcomes including HbA1c and hypoglycemia, and health care costs among T2DM patients who initiated U-500R and among those who switched from U-500R syringe administration to Kwikpen.

[2018-7241 Study Identifier] Observational Study Protocol**4. Objectives****4.1 Research Objectives****Research Objective 1: Treatment Patterns**

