- ❖ **Primary Objective 1:** Evaluate the treatment patterns of insulin including observed total daily dose [TDD] in claims, adherence, prescription fill rate, claim gaps, persistence and concomitant medication use among T2DM patients before and after U-500R syringe initiation and U-500R Kwikpen initiation separately as well as before and after U-500R device switch from syringe to Kwikpen:
 - Characterize U-500R Kwikpen patients;
 - Determine differences between treatment patterns before and after U-500R Kwikpen initiation;
 - Determine differences between treatment patterns before and after U-500R syringe initiation; and
 - Determine differences between treatment patterns before and after U-500R device switch from syringe to Kwikpen.

Research Objective 2: Treatment Outcomes

- ❖ **Primary Objective 2:** Evaluate the HbA1c level among T2DM patients before and after U-500R syringe initiation and U-500R Kwikpen initiation separately, as well as before and after U-500R device switch from syringe to Kwikpen:
 - Determine differences between HbA1c level before and after U-500R Kwikpen initiation;
 - Determine differences between HbA1c level before and after U-500R syringe initiation;
 - Determine differences between HbA1c level before and after U-500R device switch from syringe to Kwikpen; and
 - Determine whether observed TDD in claims or insulin adherence played a role in HbA1c changes among U-500R syringe initiators, U-500R Kwikpen initiators, and device switchers from syringe to Kwikpen.
- ❖ **Secondary Objective 2a:** Evaluate the hypoglycemic events among T2DM patients before and after U-500R syringe initiation and U-500R Kwikpen initiation separately, as well as before and after U-500R device switch from syringe to Kwikpen:
 - Determine differences between hypoglycemia events before and after U-500R Kwikpen initiation;
 - Determine differences between hypoglycemia events before and after U-500R syringe initiation;

[2018-7241 Study Identifier] Observational Study Protocol

- Determine differences between hypoglycemia events before and after U-500R device switch from syringe to Kwikpen; and
 - Determine whether observed TDD in claims or insulin adherence played a role in hypoglycemic events among U-500R syringe initiators, U-500R Kwikpen initiators, and device switchers from syringe to Kwikpen.

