5.3. Study Population

5.3.1 Selection Criteria

Patient selection criteria for the U-500R Syringe Initiators [Index Event 1a]:

- Include patients who had ≥ 1 prescription claim for U-500R vial during the identification period (VHA and LCED: 01JAN2014-30JUN2017; Truven: 01APR2014-30SEP2017)—the first prescription claim for U-500R vial will be designated as index Event 1a (U-500R syringe initiation), and the date will be designated as the index date;
- Include patients who had ≥ 2 claims with an ICD-9/10-CM code (Appendix 1) for T2DM in any position (primary/secondary) at any time prior to the index date;
- Exclude patients who had both T1DM and T2DM, had no oral anti-diabetic drug (OADs; Appendix 1) other than metformin, and the ratio between the number of T1DM and T2DM claims > 0.5 at any time in the study period (VHA and LCED: 01APR2013-31MAR2018; Truven: 01JUL2013-30JUN2018);
- Include patients who were aged ≥ 18 years on the index date;
- Include patients who had continuous health plan enrollment with medical and pharmacy benefits for ≥ 9 months pre- and post-index event;
- Exclude patients with no evidence of insulin including U-500R (any type; Table 2) in the 9 months pre-index period (baseline);

[2018-7241 Study Identifier] Observational Study Protocol

- Exclude patients with ≥ 1 prescription claim for U-500R use in the 9 months pre-index period;
- Include patients who had ≥ 1 prescription claim for any insulin other than U-500R in the 9-month pre-index period;
- Include patients who had ≥ 1 HbA1c measurement within 90-day pre-index or 30-day post-index event;
- Include patients who had ≥ 1 HbA1c measurement after the 30-day post-index period at any time in the 9-months follow-up period;
 - Patients with ≥ 1 HbA1c measurement after the 30-day post-index and within 30 days prior to the end of the 9-months follow-up period will be flagged; and
 - Patients with ≥ 1 HbA1c measurement after the 30-day post-index and within 2 months prior to the end of the 9-months follow-up period will be flagged;
- Exclude patients who had ≥ 1 claim with a ICD-9/10-CM code (Appendix 1) for secondary diabetes, gestational diabetes, diabetes complicating pregnancy, childbirth, or puerperium, or non-clinical diabetes at any time during the 9-month baseline period;
- Exclude patients who had claims indicating pump use (Appendix 2) in the 9-month post-index (follow-up) period;

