- Exclude patients who had claims indicating TDD above 2000 units/day at any time in the pre-index or post-index periods.

Sample selection criteria for U-500R Kwikpen Initiators [Index Event 1b]

- Include patients who had ≥ 1 prescription claim for U-500R Kwikpen administration during the identification period (VHA and LCED: 01JAN2014-30JUN2017; Truven: 01APR2014-30SEP2017)–the first prescription claim for U-500R Kwikpen administration will be designated as Index Event 1b, and the date will be designated as the index date;
- Include patients who had ≥ 2 claim with an ICD-9/10-CM code (Appendix 1) for T2DM in any position (primary/secondary) at any time prior to the index date;
- Exclude patients who had both T1DM and T2DM, had no OADs (Appendix 1) other than metformin, and the ratio between the number of T1DM and T2DM claims >0.5 at any time in the study period (VHA and LCED: 01APR2013-31MAR2018; Truven: 01JUL2013-30JUN2018);
- Include patients who were aged ≥ 18 years on the index date;
- Include patients who had continuous health plan enrollment with medical and pharmacy benefits for ≥ 9 months pre- and post-index event;

[2018-7241 Study Identifier] Observational Study Protocol

- Exclude patients with no evidence of insulin including U-500R (any type; Table 2) in the 9 months pre-index period (baseline);
- Exclude patients with ≥ 1 prescription claim for U-500 use in the 9 months pre-index period;
- Include patients who had ≥ 1 prescription claim for any insulin other than U-500R (Table 2) in the 9-month pre-index period;
- Include patients who had ≥ 1 HbA1c measurement within 90-day pre-index or 30-day post-index event;
- Include patients who had ≥ 1 HbA1c measurement after the 30-day post-index period at any time in the 9-months follow-up period;
 - Patients with ≥ 1 HbA1c measurement after the 30-day post-index and within 30 days prior to the end of the 9-months follow-up period will be flagged; and
 - Patients with ≥ 1 HbA1c measurement after the 30-day post-index and within 2 months prior to the end of the 9-months follow-up period will be flagged;
- Exclude patients who had ≥ 1 claim with a ICD-9/10-CM code (Appendix 1) for secondary diabetes, gestational diabetes, diabetes complicating pregnancy, childbirth, or puerperium, or non-clinical diabetes at any time during the 9-month baseline period;
- Exclude patients who had evidence of pump use (Appendix 2) in the 9-month follow-up period;

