- Exclude patients who had claims indicating TDD above 2000 units/day at any time in the pre-index or post-index periods.

Sample Selection Criteria for U-500R Device Switchers from Syringe to Kwikpen [Index Event 2]

- Include patients who had ≥ 1 claim for U-500R Kwikpen administration in the identification period (VHA and LCED: 01JAN2014-30JUN2017; Truven: 01APR2014-30SEP2017)–the first prescription claim for U-500R Kwikpen administration will be designated as the Index Event 2, and the date will be designated as the index date;
- Include patients who had ≥ 2 claim with an ICD-9/10-CM code (Appendix 1) for T2DM in any position (primary/secondary) at any time prior to the index date;
- Exclude patients who had both T1DM and T2DM, had no OADs (Appendix 1) other than metformin, and the ratio between the number of T1DM and T2DM claims > 0.5 at any time in the study period (VHA and LCED: 01APR2013-31MAR2018; Truven: 01JUL2013-30JUN2018);
- Include patients who were aged ≥ 18 years on the index date;
- Include patients who had continuous health plan enrollment with medical and pharmacy benefits for ≥ 9 months pre- and post-index event;
- Include patients who had ≥ 1 prescription claim for U-500R vial use in the 9-month baseline period;

[2018-7241 Study Identifier] Observational Study Protocol

- Include patients who had ≥ 1 HbA1c measurement within 90-day pre-index event or 30-day post-index event; and
- Include patients who had ≥ 1 HbA1c measurement after the 30-day post-index period;
 - Patients with ≥ 1 HbA1c measurement after the 30-day post-index and within 30 days prior to the end of the 9-months follow-up period will be flagged; and
 - Patients with ≥ 1 HbA1c measurement after the 30-day post-index and within 2 months prior to the end of the 9-months follow-up period will be flagged;
- Exclude patients who had ≥ 1 claim for U-500R Kwikpen administration in the 9-month baseline period;
- Exclude patients who had ≥ 1 claim with a ICD-9/10-CM code (Appendix 1) for secondary diabetes, gestational diabetes, diabetes complicating pregnancy, childbirth, or puerperium, or non-clinical diabetes at any time during the 9-month baseline period;
- Exclude patients who had claims indicating pump use (Appendix 2) in the identification period;
- Exclude patients who had claims indicating TDD exceeding 2000 units/day at any time in the pre-index or post-index periods.

Note:

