5.3.2 Subject Groups

After applying the inclusion and exclusion criteria, our analysis will focus on the following cohorts.

Index Event 1a

- U-500R Syringe Initiators Cohort: Patients who initiated U-500R syringe administration (index event 1a) on their index date.

Index Event 1b

- U-500R Kwikpen Initiators Cohort: Patients who initiated U-500R Kwikpen administration (index event 1b) on their index date.

Index Event 2

- U-500R Device Switchers Cohort: Patients who switched from U-500R syringe to Kwikpen will be included in this cohort.

Note: U-500R syringe/ Kwikpen initiators cohorts who were identified based on the index event 1a or 1b were U-500R naïve patients who did not have any evidence of U-500R use prior to the index date; whereas patients in U-500R device switchers cohort identified from index event 2 had been exposed to U-500R prior to the index date due to U-500R syringe use.

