		
PDC before U-500R initiation will be calculated as the number of days covered by the prescription claims of insulin (any insulin)/total days in the pre-index period;
 
PDC after U-500R initiation will be calculated as the number of days covered by the prescription claims of insulin (any insulin)/total days in the post-index period.
 
For U-500R Kwikpen initiators (index event 1b):
 
PDC before U-500R initiation will be calculated as the number of days covered by the prescription claims of insulin (any insulin)/total days in the pre-index period;
 
PDC after U-500R initiation will be calculated as the number of days covered by the prescription claims of insulin (any insulin)/total days in the post-index period.
 
For U-500R device switchers (index event 2):
 
PDC before switching will be defined as the number of days covered by the prescription claims of insulin (U-500R syringe)/total days in the pre-index period;
 
PDC after switching will be defined as the number of days covered by the prescription claims of insulin (U-500R Kwikpen)/total days in the post index period
 
Note: For the calculation of PDC in patients with evidence of a basal-bolus regimen, basal/bolus-premixed, or basal/bolus-U-500R, the overlap days will be adjusted for the concomitant use of basal and bolus insulins, but will not be adjusted within basal and within bolus insulins.

--	--	---

[2018-7241 Study Identifier] Observational Study Protocol

Persistence/time to discontinuation	Truven: Outpatient pharmacy claims table VHA: Pharmacy file	Persistence will be defined as the percentage of patients continuing on the index medication in the post-index period. Patient is considered to discontinue if there is no refill of the index medication within 60 days from the run-out date (date of last prescription + days of supply) i.e, a gap of >60 days from the run out date. The run-out date will be the discontinuation date. Time to discontinuation will be defined as the total number of days from the index date to the discontinuation date during the post-index period.
Abandonment/fill rates	Truven: Outpatient pharmacy claims table VHA: Pharmacy file	The average number of insulin prescription fills will be calculated in the pre- and post-index periods among all the study cohorts.

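### Initiators are dropped from every objective on post-index information (a pump claim, or a claim above 2000 units/day), although post-index dose is itself a primary outcome

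*Protocol*

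**What the plan says.** Section 5.3.1 lists the criteria by cohort.

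- **Pump, syringe initiators (Index Event 1a):** "Exclude patients who had claims indicating pump use (Appendix 2) in the 9-month post-index (follow-up) period".
- **Pump, Kwikpen initiators (1b):** "Exclude patients who had evidence of pump use (Appendix 2) in the 9-month follow-up period".
- **Pump, device switchers (2):** "Exclude patients who had claims indicating pump use (Appendix 2) in the identification period".
- **Dose, 1a and 1b, with near-identical wording for switchers:** "Exclude patients who had claims indicating TDD above 2000 units/day at any time in the pre-index or post-index periods".

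Neither initiator cohort is screened for pump use in the baseline period.

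Section 5.3.2 shows that these rules act before any analysis: "After applying the inclusion and exclusion criteria, our analysis will focus on the following cohorts". The note closing the criteria in Section 5.3.1 relaxes only the HbA1c requirement, and only for Truven claims. The pump and dose exclusions therefore carry into every objective. The protocol gives no reason for either rule.

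Primary Objective 1 (Section 4.1) is to "Evaluate the treatment patterns of insulin including observed total daily dose [TDD] in claims, adherence, prescription fill rate, claim gaps, persistence and concomitant medication use". In Section 5.5, Table 3, TDD is total insulin units over unique days of supply, calculated before and after index. Persistence is worded as: "Persistence will be defined as the percentage of patients continuing on the index medication in the post-index period". Discontinuation is a gap of more than 60 days after run-out. Section 3 notes that "off-label continuous subcutaneous insulin infusion (CSII) administration has been employed increasingly for the administration of U-500R".

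**The concern.** Cohort entry should rest on what is known at index. Here it depends on what happens in the next nine months, in two ways.

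The dose rule truncates a primary outcome from above, and the deletion reaches further than that outcome. One claim with a wrong quantity or days of supply removes the patient's HbA1c, hypoglycemia and cost results, none of which are calculated from that claim's daily dose.

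The pump rule removes patients who depart after index from the syringe or Kwikpen exposure defined in Table 3. Because initiators have no baseline pump screen, the pre-index period may contain pump use while the post-index period cannot. In a before/after design, that one-sided rule alters the contrast under test.

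**Working it through.** The protocol states no pump rate, discontinuation rate, TDD distribution or share above 2000 units/day, so there is no figure of its own to reproduce. Table 4 holds raw VHA counts only. The first two steps compare text; the others are illustrations on assumed inputs.

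**1. Dose rule against outcome.** The excluded quantity (TDD) and the outcome (TDD) are the same variable, so the selection is literal. The exclusion reads as claim-level because it applies at any time, whereas the Table 3 outcome is a period average. A patient with an ordinary average can therefore be lost for one record. TDD is also a covariate in the adherence, HbA1c, hypoglycemia and cost models in Section 6.4.1.

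**2. Pump windows.** Initiators are screened over the nine follow-up months. Switchers are screened over a calendar window, which for VHA and LCED runs from 01JAN2014 to 30JUN2017.
- A switcher indexed on 1 June 2017 has about one month of the nine screened.
- A switcher indexed on 30 June 2016 finishes follow-up at the end of March 2017, yet a pump claim in April to June 2017 still excludes.

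**3. Persistence.** Let P be persistence among retained patients and q the share of the full cohort excluded for pump claims. With those patients restored, persistence is P(1 − q) if all count as discontinued, and P(1 − q) + q if all count as persistent. For assumed P = 60%:

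| q | all discontinued | all persistent |
|---|---|---|
| 1% | 59.4% | 60.4% |
| 3% | 58.2% | 61.2% |
| 5% | 57.0% | 62.0% |
| 10% | 54.0% | 64.0% |

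For P from 50% to 70% and q from 1% to 10%, the reported figure is too high by 0.5 to 7 points in the first case and too low by 0.3 to 5 points in the second.

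**4. Mean post-index TDD, period average truncated.** Assume a lognormal with mean m and coefficient of variation CV. Then s² = ln(1 + CV²), μ = ln m − s²/2, and the mean after truncation is m·Φ((ln 2000 − μ − s²)/s) / Φ((ln 2000 − μ)/s). Reduction in units/day:

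| m | CV 0.5 | CV 0.8 | CV 1.2 |
|---|---|---|---|
| 250 | 0.0 | 1.0 | 9.6 |
| 350 | 0.1 | 5.1 | 26.4 |
| 500 | 1.4 | 21.5 | 68.6 |

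Six of the nine cells are below 10.

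**5. Mean post-index TDD, claim-level rule.** Suppose a share q of patients with period mean D is deleted and the rest average 300. The reported mean falls by q(D − 300). For q = 0.5% and D = 800 this is 0.005 × 500 = 2.5. For q = 2% and D = 2000 it is 0.02 × 1700 = 34.

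**6. Does concentration make the limit uneven?** In volume, 2000 units/day is 2000/500 = 4 mL of U-500R or 2000/100 = 20 mL of U-100. But the limit is in units. If a true supply of s days at dose D is recorded as s′ days, the claimed TDD is D·s/s′, and concentration drops out. Section 3 itself says U-500R gives a corresponding dose in 20% of the volume.

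**The case against.** **The pump rule classifies exposure.** Cohort 1a is identified by a vial claim, which cannot show whether the insulin goes into a syringe or a pump. Post-index pump claims are the listed criterion that separates the two. Screening baseline only would admit people who start U-500R by pump as syringe initiators and then record them as early discontinuers. This stands for pump claims at or near index; it is weaker for a first pump claim months later. The rule also removes established pump users with post-index claims, so it is not purely a screen on starting a pump.

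**Persistence is not shown to be too high.** A reader might infer that deleting pump patients must inflate persistence. The definition does not support that, because it tracks refills of the index medication and does not mention pumps. A vial initiator who keeps filling vials for a pump remains persistent, so deleting that patient pushes the figure down. Upward bias is likelier for Kwikpen initiators who stop filling pens.

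**The dose limit does not fall five times harder on U-500R.** The volumes in step 6 might suggest it, but at equal unit dose the asymmetry disappears. The rule also covers both periods, so part of any truncation cancels in the before/after difference.

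**The dose rule may be a plausibility filter.** The limit is ten times the 200 units/day that Section 3 uses for severe insulin resistance, so few genuine values may exceed it. That is a fair reading, but a filter on records does not require deleting the patient. Part of the objection does hold: if days of supply is the faulty field, that claim's contribution to PDC and run-out date is suspect too.

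**Some of this may be handled elsewhere.** Attrition counts and sensitivity analyses may sit in the table shells or a statistical analysis plan, which are not visible here. The eligibility rules themselves are fixed in the protocol.

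**Conclusion.** The point holds as a minor design weakness. For dose it is direct: patients are selected on the value of a primary outcome and lose valid data on other outcomes. For pump use, the rule selects on post-index departure from the exposure, lacks a baseline counterpart for initiators, and does not match the switcher window.

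The direction for persistence is uncertain and may differ between cohorts: likely upward for Kwikpen initiators who leave the pen, possibly downward for vial initiators who keep refilling. The size cannot be obtained from the protocol. The ranges above rest entirely on assumed pump shares, persistence levels and dose distributions, and the effect is probably small. The case for acting is that the change is cheap.

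**What to change.** 1. **Dose.** In Section 5.3.1, replace whole-patient exclusion above 2000 units/day with a record-level rule. Set the affected TDD and ADD to missing, or to a stated cap, in the dose analyses and in models that use TDD, and keep the patient for all other outcomes. Say whether the limit applies to a claim or to the period average, and how PDC and run-out date treat a claim whose days of supply is suspect.
2. **Pump.** Reconcile the windows across the three cohorts and add a baseline pump screen for initiators. For the vial cohort, keep pump claims at or near index as an exposure-classification exclusion, with the window stated.
3. **Sensitivity analysis.** Retain patients whose first pump claim comes later in follow-up, censored at that date. Show persistence both ways: pump start counted as leaving the device, and refill-based as now defined. Report the number removed by each rule.

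The cost is revised eligibility wording and some programming on data already held. With missing rather than capped TDD, models adjusting for TDD lose a few patient-periods, so their record counts will be slightly below those of the unadjusted comparisons.

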5.1 Summary of Research Design

This will be a retrospective cohort study using the Veterans Health Administration (VHA) database, linked Truven MarketScan Claims and Electronic Medical Records [EMR] Data (LCED), as well as the Truven MarketScan claims databases (Table 1).

Multiple datasets will be used due to unavailability of the certain study outcomes in one single dataset. (e.g. out-of-pocket costs are not available in VHA dataset; HbA1c not available in Truven claims dataset). Additionally, using multiple datasets will improve the generalizability of the study, and since U-500R Kwikpen is recently available in the market, linking two databases would ensure that the study has adequate sample size. Furthermore, the patient population in the VHA primarily consists of veterans across the country (non-commercial database), whereas Truven is an employment-based health insurance (commercial database). Therefore, conducting the analysis separately in each of these databases as well as in the pooled dataset would give a more comprehensive and complete picture of the treatment patterns and outcomes in the real-world in this patient population.

To meet the analytical requirement of multiple research objectives, the following criteria will be used:

- The first prescription claim date for U-500R syringe or U-500R Kwikpen administration will be considered U-500R initiation and designated as Index Event 1 (syringe: Index Event 1a; Kwikpen: Index Event 1b).
- The date for U-500R device switch from syringe to Kwikpen will be designated as Index Event 2.
- The study period will range from 01APR2013-31MAR2018 for VHA and LCED; and 01JUL2013-30JUN2018 for Truven MarketScan claims.
- The identification period will be 01JAN2014-30JUN2017 for VHA and LCED; and 01APR2014-30SEP2017 for Truven MarketScan claims; the baseline and follow-up periods will be 9 months pre- and 9 months post-index date, respectively (Figures 1-3).

[2018-7241 Study Identifier] Observational Study Protocol**Table 1 Study Design by Objectives**

Research Objectives	Database (study period)	Study Cohorts
Research Objective 1		
Primary Objective 1	
 • VHA (01APR2013-31MAR2018) • Pooled VHA and LCED (01APR2013-31MAR2018) • Truven MarketScan Claims Database (01JUL2013-30JUN2018) 	U-500R syringe initiators U-500R Kwikpen initiators U-500R device switchers
Research Objective 2		

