All-cause health care total and out-of-pocket costs	Truven: Inpatient service table, outpatient service table, outpatient pharmacy claims table	All-cause health care costs for total and out-of-pocket costs including inpatient costs, outpatient costs, pharmacy costs, total costs (inpatient + outpatient + pharmacy), out-of-pocket inpatient costs, out-of-pocket outpatient costs, out-of-pocket pharmacy costs and total out-of-pocket costs (inpatient + outpatient + pharmacy) will be computed among T2DM patients before and after U-500R syringe initiation and U-500R Kwikpen initiation. Costs will be adjusted to 2018 US dollars using the annual medical care and drug costs components of the Consumer Price Index (CPI) to reflect inflation.
---	---	--

Note: When comparing the TDD, ADD, adherence, fill rates and claim gaps in the pre vs post-index periods among the U-500R device switchers, only the claims corresponding to U-500R (syringe in the pre-index and Kwikpen in the post-index) will be considered. To be more specific we will be looking only at the treatment patterns of U-500R alone rather than the regimen.

However, for the U-500R initiators, the regimen use (use of different types of insulin) in the pre-index period will be compared to the regimen use (U-500R + other insulins) in the post-index period.

[2018-7241 Study Identifier] Observational Study Protocol**6. Sample Size and Statistical Methods****6.1 Determination of Sample Size**

The preliminary sample sizes for the VHA databases from 2013-2018 are shown below. This study will use the most recently available 5 years of data.

Table 4. Preliminary Sample Size

Database	Counts
VHA (01APRIL2013-31MARCH2018)	
T2DM (ICD-9: 250.x0, 250.x2) + Humulin R U-500 Kwikpen (NDC: 00002882427, 00002882459)	4,120
≥2 HbA1c measurements	4,066
T2DM + Humulin R U-500 Vial (NDC: 00002850101)	5,863
≥2 HbA1c measurements	5,718

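### Both initiator cohorts are screened for pump claims only after the index date, so claims-identified pump use, and in Primary Objective 3 billed pump cost, can fall only on the before side

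*Protocol*

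**What the plan says.** All pump rules are in section 5.3.1 of the protocol.

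- Syringe initiators (Index Event 1a): "Exclude patients who had claims indicating pump use (Appendix 2) in the 9-month post-index (follow-up) period".
- Kwikpen initiators (Index Event 1b): "Exclude patients who had evidence of pump use (Appendix 2) in the 9-month follow-up period".
- Device switchers (Index Event 2): "Exclude patients who had claims indicating pump use (Appendix 2) in the identification period".

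Section 5.1 sets the comparison windows: "the baseline and follow-up periods will be 9 months pre- and 9 months post-index date, respectively". The baseline insulin rule for initiators does not restrict how insulin was delivered: "Include patients who had ≥ 1 prescription claim for any insulin other than U-500R in the 9-month pre-index period". Another exclusion in the same lists covers both windows: "Exclude patients who had claims indicating TDD above 2000 units/day at any time in the pre-index or post-index periods".

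The cost outcome in Table 3 (section 5.5) is broad: "All-cause health care costs for total and out-of-pocket costs including inpatient costs, outpatient costs, pharmacy costs", plus totals and the out-of-pocket counterparts. Pump equipment and supplies are not separated out. The covariate lists in section 6.4.1 for the adherence, HbA1c, hypoglycemia and cost models do not include pump use.

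**The concern.** Every initiator analysis compares a patient with himself or herself before and after the index date, with no control group. If eligibility allows a feature in one window and forbids it in the other, the feature contributes to the difference through selection alone. Pump delivery is such a feature for Index Events 1a and 1b.

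Two things are at stake. First, for retained former pump users, changes in dose, adherence, HbA1c and hypoglycemia reflect two changes at once: the end of pump use and the start of U-500R. Second, in Primary Objective 3 (Truven claims, initiators only), pump-related payments and patient cost shares can enter the before total but not the after total. The mediation sections for HbA1c and costs treat the pre/post indicator as the impact of the index event, so a reader would credit U-500R with whatever this selection adds.

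**Working it through.** No power or sample-size formula applies, and the protocol has no figure on this point to reproduce. The check sets the eligibility rules against the two windows.

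**Step 1. Months screened, initiators.** Baseline: 0 of 9. Follow-up: 9 of 9.

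**Step 2. The four possible claim patterns, initiators.**

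| Pump claim in baseline | Pump claim in follow-up | Result |
|---|---|---|
| No | No | Kept |
| Yes | No | Kept |
| No | Yes | Removed |
| Yes | Yes | Removed |

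Only one kept pattern contains pump claims, and it has them before index only.

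**Step 3. Effect on the mean cost contrast.** Let *a*, *s* and *b* be the shares of otherwise eligible initiators with pump claims only before, only after, and in both windows. Let *C* be the pump-related cost per user per 9-month window, taken as equal in both.

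- Without any pump rule, the pump contribution to after minus before is (*s* + *b*)*C* − (*a* + *b*)*C* = (*s* − *a*)*C*, which can have either sign.
- Under the protocol's rule, *s* and *b* are removed. The contribution is −*pC*, with *p* = *a*/(1 − *b* − *s*). It cannot be positive.
- With baseline screened as well, *p* = 0 and the contribution is 0.

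**Step 4. Illustrative size.** The protocol gives neither *p* nor *C*. The values below are assumptions that show scale only (downward shift per patient, *p* × *C*).

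| *p* | *C* = $1,000 | *C* = $3,000 | *C* = $6,000 |
|---|---|---|---|
| 1% | $10 | $30 | $60 |
| 5% | $50 | $150 | $300 |
| 10% | $100 | $300 | $600 |

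The protocol offers no basis for a comparable figure for HbA1c, dose or hypoglycemia.

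**Step 5. Device switchers.** Their pump screen is the calendar identification period, which lasts 42 months in each database (January 2014 to June 2017; April 2014 to September 2017).

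- Index date on the first day: none of the baseline and all of the follow-up is screened.
- Index date on the last day: all of the baseline and none of the follow-up is screened.
- Index date at least 9 months from both ends (42 − 9 − 9 = 24 months of possible dates): both windows are fully screened.

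The gap for switchers can therefore fall on either side. The calendar rule can also remove a patient for a pump claim that lies outside that patient's own two windows.

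**Step 6. Repair elsewhere.** The protocol states no baseline criterion, model covariate, cost carve-out or sensitivity analysis that would offset the initiator rule.

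**The case against.** The follow-up screen has an evident purpose. Section 3 notes growing off-label pump delivery of U-500R, and Index Event 1a is identified by a vial claim but labelled syringe initiation. Removing post-index pump users keeps pump-delivered U-500R out of that cohort. Baseline exposure is deliberately broad, and a move from pump insulin to U-500R injection fits the stated regimen comparison. This explains why follow-up is screened. It does not explain why baseline is not.

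A patient who truly left the pump also stopped incurring its cost, and an all-cause total is meant to capture that. A reader might call the whole shift an artificial saving; the documents do not support that. What stands is that the rule keeps pump stoppers, removes continuers and starters, and leaves two changes mixed in those kept.

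Most objectives are worded as differences or associations rather than effects. That is fair, and the impact reading is confined to the mediation sections.

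Three stronger readings are tempting and fail:

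- That every comparison in the study is affected in this direction. Switchers have another rule, and pump costs reach only Primary Objective 3.
- That retained patients left the pump at the moment U-500R began. Their pump claims need only have stopped by the index date and may have ended months earlier.
- That the secondary-diabetes and pregnancy exclusion, which applies "or non-clinical diabetes at any time during the 9-month baseline period", is a mirror-image fault. A baseline-only exclusion is conventional and avoids selecting on later events.

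**Conclusion.** The point holds for the two initiator cohorts. The one-sided window follows from the text of section 5.3.1, and its direction does not depend on any assumption about prevalence: claims-identified pump use, and billed pump cost in Primary Objective 3, can appear only before index. The rule acts on claims, so pump delivery that leaves no claim could remain on either side.

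The size is unknown. The $10 to $600 range rests wholly on assumed shares and costs, and the protocol gives no mean total cost against which to judge it. The effect may be small if few initiators used a pump. The case for acting is that the direction is known, nothing else in the protocol offsets it, and the correction is cheap. The difference between the initiator and switcher pump windows is unexplained and should be reconciled at the same time.

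**What to change.** In section 5.3.1, extend the Appendix 2 pump exclusion for Index Events 1a and 1b to the 9-month baseline as well as the 9-month follow-up. Replace the calendar window for Index Event 2 with the same patient-level pre- and post-index periods, so that all three cohorts share one rule.

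If the sponsor prefers to keep former pump users, the minimum is to report the number of initiators with baseline pump claims in each database and repeat the before/after analyses without them.

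The cost is one more filter on an existing code list and a presumably small loss of patients who moved from a pump to U-500R injection. For initiators the added filter uses baseline information only, so it introduces no further selection on post-index events.
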